2.5.4.2 Analysis of uncorrected ACPR rate using Kaplan-Meier method

For the FAS, the proportion of patients with uncorrected ACPR at Day 29 and 95% CI will be also estimated using the Kaplan-Meier method ([Stepniewska and White 2006](#) and [WHO 2015](#))

Event = PCR-uncorrected non-responder during the study (same as at Day 15, Day 43, See [Section 2.1](#)). The event time is the first time when the patient becomes a non-responder without PCR-correction. If a patient parasite is not cleared at all, Day 7 is considered as the event time.

The uncorrected ACPR rate at Day 29 is estimated by the survivor function at Day 29.

Rule for censoring:

The following censoring rules will be applied to the patients who were not non-responders

- Patients who cleared the initial infection by Day 7 and are re-infected with species different than *P. Falciparum* will be censored at the time of re-infection.
- Patients who received non-rescue anti-malaria medication will be censored at the first time of anti-malaria medication;
- other patients will be censored at the time of last parasitemia assessment.

An asymptotic two-sided 95% CI for the difference in proportion of responders between each KAF156/LUM-SDF combination treatment group and Coartem[®] will be calculated from the z-test statistic distribution based on the variance of individual proportion using the Greenwood formula.

The confidence interval will be constructed as: $(r_k - r_c) \pm Z_{\alpha/2} * SE_d$,

where,

I_T = Kaplan-Meier estimate for the investigational group at time t,

I_C = Kaplan-Meier estimate for the control group at time t,

$SE_d = \sqrt{(SE_k^2 + SE_c^2)}$,

SE_T = estimated standard error for the investigational group based on Greenwood's formula,

SE_C = estimated standard error for the control group based on Greenwood's formula,

$Z_{\alpha/2}$ = z-statistic = $\text{probit}(1 - \alpha/2)$ from a normal distribution function,

$\alpha = 0.05$.

2.6 Analysis of the key secondary objective

There is no key secondary objective in this study.

2.7 Analysis of secondary efficacy objective(s)

2.7.1 Secondary endpoints

Secondary efficacy variables include:

1. PCR-corrected ACPR at Days 15 and 43;
2. Uncorrected ACPR at Days 15, 29, and 43;

3. Proportion of patients with parasitemia at 12, 24, and 48 hours after treatment;
4. Time to parasite clearance (PCT), defined as time from the first dose until the first total and continued disappearance of (*P. Falciparum*) asexual parasite forms which remained at least a further 48 hours;
5. Time to fever clearance (FCT), defined as time from the first dose until the first time the axillary body temperature decreased below and remained below 37.5°C axillary or 38.0°C oral/tympanic/rectal for at least a further 24 hours;
6. Proportion of patients with early treatment failure (ETF);
7. Proportion of patients with late clinical failure (LCF);
8. Proportion of patients with late parasitological failure (LPF);
9. Incidence rate of recrudescence and reinfection at Days 15, 29 and 43.

Analyses of ACPRs (PCR corrected or uncorrected) will be based on the FAS and PPS. Analyses of other secondary efficacy variables will be based on the FAS.

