2.5.2 Statistical hypothesis, model, and method of analysis

The statistical null hypothesis is that the ACPR rate at Day 29 is at most 80% with the alternative hypothesis that the ACPR rate at Day 29 is greater than 80%. The statistical hypothesis will be evaluated using the lower limit of 2-sided 95% exact confidence interval (CI) (Pearson-Clopper method) for the ACPR rate at Day 29. If the lower limit of 2-sided 95% exact confidence interval for the ACPR rate at Day 29 is greater than 80%, the null hypothesis will be rejected. The statistical hypothesis testing will be evaluated separately for each KAF156 and LUM-SDF combination in each part based on the PPS. There is no adjustment for multiplicity since this is an exploratory study.

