2.7.2.1 PCR-corrected ACPR and uncorrected ACPR

At each visit, the ACPR rate with 95% confidence intervals will be provided using Pearson-Clopper method for each treatment group.

Handling of missing values/censoring/discontinuations

Data will be handled as follows for ACPRs (PCR corrected or uncorrected):

- Presence of parasitemia which were determined to be reinfection on Day 8 or later will be counted as responders for PCR corrected ACPR and as non-responder for PCR uncorrected ACPR from the day of test
- Presence of parasitemia which cannot be determined to be recrudescence or reinfection due to missing PCR data will be counted as non-responders from the day of test
- Missing/underdetermined responses at a visit due to missing blood smear data at the visit will be counted as non-responders (PCR corrected or uncorrected) unless there is a later blood smear test indicating no parasitemia
- Patients who received non rescue anti-malarial medication will be considered in the analysis as if they had not taken the antmalarial drug

In addition, PCR-corrected and uncorrected ACPR rate will be calculated and plotted using the Kaplan-Meier method for each treatment group in the FAS (see [Section 2.5.4](#)).

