Vital signs (clinical notable)	Safety	Yes	Yes
Early treatment failures	Safety	Yes	Yes
Efficacy			
PCR corrected and uncorrected cure rates at Day 29	Per-Protocol	No	Yes
PCR corrected and uncorrected cure rates at Day 43	Per-Protocol	No	Yes
PCT, FCT	FAS	No	Yes
KAF156 and LUM-SDF PK	PK	No	Yes

3 Sample size calculation

Sample size for PK run-in cohort

The objective of this part is to assess the effect of LUM-SDF in the exposure of KAF156 in patients and to see if the current planned dosages for KAF156 in Part A should be modified or how to modify KAF156 dosages in Part A. Therefore, the sample size is calculated/justified based on the precision of estimating KAF156 exposure. The key variables for exposure of KAF156 are AUC_{0-24h} and C_{max} . It's well known that the distribution of AUC or C_{max} is best described by log normal distribution. The half width of 2-sided 90% confidence interval for the log AUC_{0-24h} or log C_{max} is the target for sample size calculation. The relevant historical data for sample size calculation are the standard deviations of log AUC_{0-24h} and log C_{max} , which are usually invariant to the dosage.

In POC Study X2202, the standard deviation for log AUC_{0-24h} was 0.26 and 0.27 for 10 *P. falciparum* patients treated with KAF156 400 mg QD 3 days and for 18 *P. falciparum* patients

treated with KAF156 800 mg QD, respectively. The corresponding standard deviation for log C_{max} was 0.205 and 0.215, respectively.

Table 3-1 Sample size and width of 2-sided 90% CI for log AUC_{0-24h} and log C_{max}

Standard deviation (in log)	n	Target half width of 2-sided 90% CI	Probability that observed half width of 2-sided 90% CI is ≤ the target
0.21	9	0.153	0.80
0.21	12	0.126	0.80
0.21	10	0.150	0.80
0.26	9	0.200	0.80
0.26	12	0.155	0.80
0.26	13	0.150	0.80
0.26	12	0.150	0.70
0.27	9	0.200	0.80
0.27	12	0.161	0.80
0.27	14	0.150	0.80
0.27	12	0.150	0.68

Based on nQuery Table MOC1-1.nqa.

A sample size of 12 patients will provide 80% probability that the observed half width of 2-sided 90% CI for log AUC_{0-24h} is ≤0.155. A sample size of 12 patients will provide 80% probability that the observed half width of 2-sided 90% CI for log C_{max} is ≤0.126.

Part A

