The primary efficacy objective for this part is to determine the effective dose(s) of KAF156 combined with LUM-SDF for treatment of uncomplicated malaria caused by *P. falciparum* in adolescents and adults. The primary efficacy endpoint is the PCR corrected ACPR rate at Day 29 based on the per-protocol analysis set. The statistical null hypothesis is that the ACPR rate is at most 80% with the alternative hypothesis that the ACPR rate is greater than 80%. The statistical hypothesis will be evaluated using the lower limit of 2-sided 95% exact confidence interval for the ACPR rate. If the lower limit of 2-sided 95% exact confidence interval for ACPR rate is greater than 80%, the null hypothesis will be rejected.

Rejecting the null hypothesis of at most 80% ACPR rate is equivalent to showing non-inferiority to a ACPR rate of 90% with a non-inferiority margin of 10%. 90% is specified in the [2015 WHO guidelines](#) as the ACPR rate cutoff-threshold for a change in treatment policy and a 10% non-inferiority margin is considered as acceptable for early-phase trials ([Held, et al 2015](#)).

[figure not shown]
[Figure 3-1](#) plots the power to reject the null hypothesis of at most 80% ACPR rate versus sample size by various true ACPR rates (90%, 93%, 95%, and 97%). Due to the discrete property of binomial distribution, the power increases zigzag with jump at 26, 34, 41, 48, 55, 62, and 68 as the sample size increases. When the sample size is at least 41, the power to reject the null hypothesis of at most 80% ACPR rate is about 80% or higher if the true rate is 95% or higher.

Since there is a 2:1 ratio among different treatment groups, the sample size in the per-protocol analysis set will be targeted to be 42 patients for each KAF156/LUM-SDF dose combination

group and 21 patients for the comparator (Coartem[®]) cohort. This sample size will provide at least 80% power to reject the null hypothesis of at most 80% ACPR rate for the 6 KAF156 dose combinations if the true ACPR rate is at least 95%. If there are multiple KAF156/LUM-SDF dose combinations that are all effective, the less frequent or/and highest KAF156/LUM-SDF dose combination(s) that is tolerable may be selected for further evaluation. The PK/PD modeling may be used to assist the selection of appropriate dose combination(s) for Part B.

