5.7 Rule of exclusion criteria of analysis sets

Table 5-10 Protocol deviations and non-PD criteria leading to exclusion from analysis sets

Analysis Set	PD (Description and ID) that causes Patients to be excluded	Non-PD criteria that cause Patients to be excluded
Randomized	
 Informed Consent for study participation or parental consent not obtained and patient entered trial (INCL01) 	
 Not randomized (Parts A and B) Misrandomized if identified from IRT (Parts A and B) Not treated with study medication (PK run-in part)
FAS	NA	
 Not in Randomized set; Baseline parasitemia count is 0 or missing No study drug taken
PPS	
 Parasite specie is other than Plasmodium falciparum OR mixed infection (INCL04) Baseline plasmodium falciparum parasite count <1000/uL or >=150000/uL at screening visit (INCL05) No fever within the past 24 hours at baseline (INCL07) Prohibited non-antimalarial medications that may have effect on efficacy (PROH01b) if received before the Day 29 visit without being treatment failures 	
 Not in FAS; <80% of randomized study medication taken Received non-study concomitant antimalarial drugs prior to Day 29 without experiencing treatment failure Not classified as non-responder before Day 8, no positive blood smear parasite on Day 8 onwards, and blood smear parasite result is missing at Day 29 and later (early discontinued) Not classified as non-responder before Day 8, have at least one positive blood smear parasite result between Day 8 and Day 29 which cannot be determined as recrudescence or new infection based on PCR genotyping and have parasites cleared prior to the positive blood smear parasite;

		
 Not classified as non-responder before Day 8, no positive blood smear parasite before Day 29, blood smear parasite result is missing at Day 29, and blood smear parasite result is not negative at Day 43 (intermediate missing)
SAF	NA	
 Not in Randomized set; No study drug taken
PK	Patients who received concomitant prohibited medication which found to be change in the exposure that impacts interaction in PK parameters; will be reviewed case by case for exclusion from the PK set	
 Not in SAF No evaluable pharmacokinetic parameter data Compliance is <80% of randomized study medication taken

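### Uncorrected ACPR on the per-protocol set reads too high, because a PCR-evaluability rule removes patients already known to have failed

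*SAP*

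**What the plan says.** SAP 2.7.1 sets the populations for all corrected and uncorrected ACPR analyses: "Analyses of ACPRs (PCR corrected or uncorrected) will be based on the FAS and PPS". Protocol 9.5.1 says the same.

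The PPS is defined once, in SAP 2.2 and Table 5-10 (section 5.7). One Table 5-10 row excludes patients who were not non-responders before Day 8, had cleared their parasites, and then "have at least one positive blood smear parasite result between Day 8 and Day 29 which cannot be determined as recrudescence or new infection". A second row, labelled intermediate missing, excludes patients with no positive smear before Day 29, no Day 29 smear, and a Day 43 smear that is anything other than negative.

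SAP 2.1.1.1 defines late clinical failure (LCF) and late parasitological failure (LPF) from smear, temperature and clinical signs. SAP 2.1.1.2 makes any LCF or LPF up to the visit an uncorrected non-response. Neither section asks for a genotype.

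For missing smears, SAP 2.7.2.1 says "Missing/underdetermined responses at a visit due to missing blood smear data at the visit will be counted as non-responders" unless a later smear is negative. It does not restrict this rule to the FAS.

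For the DMC, Table 2-8 (section 2.15) lists the Day 29 rates and "PCR corrected and uncorrected cure rates at Day 43", both on the per-protocol set and on no other.

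**The concern.** An undetermined genotype is a reason to call the PCR-corrected outcome unevaluable. It says nothing against the uncorrected outcome, which is settled once the smear is positive. Using the same exclusion for both endpoints therefore removes only failures from the uncorrected analysis. The error has one direction and grows with the number of recurrences.

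Uncorrected ACPR at Day 29 is one of the endpoints named for the Part A interim assessment (SAP 1.1 and 2.15), and protocol 3.3 allows secondary efficacy to help separate cohorts if needed. With about 42 PPS patients per arm, one or two missing failures visibly change a rate.

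**Working it through.** **1. The plan's own figure.** The rule in SAP 2.5.2 is: "If the lower limit of 2-sided 95% exact confidence interval for the ACPR rate at Day 29 is greater than 80" per cent, reject. In SAP section 3, "the sample size in the per-protocol analysis set will be targeted to be 42 patients for each KAF156/LUM-SDF dose combination" group, and "This sample size will provide at least 80% power to reject the null hypothesis of at most 80% ACPR rate" "if the true ACPR rate is at least 95" per cent. By exact binomial calculation, n = 42 needs at least 39 responders; power at a true 95% is 0.843 and the one-sided error at 80% is 0.021. For n = 41 the threshold is 38 and power is 0.853. Allowing for 16% exclusions, 42/0.84 = 50 per arm, 21/0.84 = 25, and 6 × 50 + 25 = 325. The stated power holds. It concerns PCR-corrected ACPR at Day 29, which this point does not alter.

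**2. Who is removed.**

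| Patient | Uncorrected status (2.1.1.2) | PPS (Table 5-10) |
|---|---|---|
| Cleared, positive Day 8-29, recrudescence or new infection | Non-responder | Kept |
| Cleared, positive Day 8-29, genotype undetermined | Non-responder | Removed |
| Never cleared, positive on Day 8 or later | Non-responder | Kept, 2.2(d) |
| Day 29 missing, positive at Day 43 | Non-responder at Day 43 | Removed |

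A negative PCR result is not undetermined: SAP 2.1.1.2 makes that patient a corrected responder. The second row of the table is the source of the bias at Days 29 and 43; the fourth adds to it at Day 43.

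The exclusion rests on Table 5-10. SAP 2.2 requires only one of its criteria (a) to (d), and (b) is satisfied by a negative smear at Day 29 or later. An undetermined recurrence that is rescued and later negative could enter through (b), although Table 5-10 excludes it.

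**3. Size at Day 29.** Let r be the proportion who recur after clearance and u the proportion of recurrences that are undetermined, with no other failures. The correct uncorrected rate is 1 − r. The PPS rate is (1 − r)/(1 − ru). The documents give neither r nor u, so both ranges are assumed.

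| r | u | Correct | PPS | Overstatement (points) |
|---|---|---|---|---|
| 0.15 | 0.10 | 85.0% | 0.85/0.985 = 86.3% | 1.3 |
| 0.15 | 0.20 | 85.0% | 0.85/0.97 = 87.6% | 2.6 |
| 0.30 | 0.10 | 70.0% | 0.70/0.97 = 72.2% | 2.2 |
| 0.30 | 0.20 | 70.0% | 0.70/0.94 = 74.5% | 4.5 |

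At u = 0.20 in both arms, a 15-point difference (85% against 70%) shows as 87.6 − 74.5 = 13.1 points. The arm with more recurrences gains more.

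**4. In patients.** Suppose the PPS shows 39/42 = 92.9% (exact 95% CI 80.5-98.5). Restoring k undetermined failures gives:

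- k = 1: 39/43 = 90.7% (77.9-97.4)
- k = 2: 39/44 = 88.6% (75.4-96.2)
- k = 4: 39/46 = 84.8% (71.1-93.7)

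**5. Day 43 losses.** A patient lost before Day 29 is excluded from the PPS. A patient negative at Day 29 with no later smear stays in and is a non-responder at Day 43. Starting from 40/42 = 95.2%, losing two responders gives 38/42 = 90.5% (77.4-97.3) on the PPS, against 38/40 = 95.0% (83.1-99.4) among patients with a Day 43 result. Losing four gives 36/42 = 85.7% against 36/38 = 94.7%. The loss counts are illustrative; the documents give no loss rate between Day 29 and Day 43.

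**The case against.** The plan does not rely on the PPS alone. On the FAS, SAP 2.7.2.1 counts undetermined positives as non-responders, which is right for uncorrected ACPR. The FAS Kaplan-Meier analyses (2.5.4.1 and 2.5.4.2, listed for all three visits in Table 2-6) censor losses, and the uncorrected one counts these recurrences as events. A further FAS sensitivity analysis of uncorrected ACPR at Day 29 is in 2.7.2.2. All of this stands: a reader of the full report can find a sound figure. It does not repair the PPS figure, and Table 2-8 does not list the FAS versions.

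A reader might infer that the choice of Part B regimens rests on an inflated rate. The documents do not support that. Protocol Table 3-2 selects on PCR-corrected ACPR at Day 29 together with safety. SAP 2.15 has the study biostatistics team analyse uncorrected ACPR without naming a set, so both sets in 2.7.1 apply. Table 2-8 covers the DMC, whose stated task in protocol 8.4 is patient safety.

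A reader might also infer that scoring Day 43 losses as failures is itself an error. It is a stated, conservative rule, also in protocol 9.5.1.1. A complete-case Day 43 set would read too high if patients who are failing are the ones lost. What stands is the inconsistency: the PPS treats losses before and after Day 29 differently. Likewise, a recurrence after Day 29 with undetermined genotype is a true uncorrected failure; counting it as one is an artefact only for corrected ACPR.

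**Conclusion.** The concern holds for uncorrected ACPR on the PPS. Table 5-10 removes known failures and no successes, so the Day 29 and Day 43 rates are biased upward; the intermediate-missing row adds to this at Day 43. The Day 29 overstatement is about 1.3 to 4.5 points if 15-30% recur and 10-20% of recurrences are undetermined. The direction follows from the text; the size rests wholly on those assumed ranges, and would be smaller if 2.2(b) were taken to readmit patients who later turn negative.

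It would be wrong to read this as every recurrence being removed: genotyped recurrences and uncleared patients stay in. Nor are the primary analysis and its power affected. The secondary endpoints carry no hypothesis (SAP 2.7.2), so no formal test changes. At Day 43 the finding is one of interpretation: a fall in the PPS rate from Day 29 mixes late failure with loss to follow-up.

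**What to change.** - For uncorrected ACPR, do not apply the PCR-evaluability row of Table 5-10. Keep every smear-positive patient who meets the other PPS conditions as a non-responder from the day of the positive smear. At Day 43 this includes patients with Day 29 missing and Day 43 positive.
- Reconcile SAP 2.2(b) and (c) with Table 5-10, so that the status of an undetermined recurrence followed by a negative smear is the same in both places.
- Add FAS rows to Table 2-8, including Kaplan-Meier estimates, for corrected and uncorrected ACPR at Days 29 and 43.
- For Day 43, state that losses after Day 29 count as failures on the PPS while earlier losses are excluded, and present that rate beside the planned FAS Kaplan-Meier estimate. A complete-case Day 43 PPS is not needed.

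The cost is SAP wording, an extra population flag and a few table rows, with no new data. The drawback is that PPS denominators will differ between corrected and uncorrected ACPR, so each table should state its own.

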2.7.2 Statistical hypothesis, model, and method of analysis

There are no pre-specified hypotheses for secondary endpoints. Model, method of analysis, and handling of missing values/censoring/discontinuations are presented in the following subsections by topic.

2.7.2.1 PCR-corrected ACPR and uncorrected ACPR

At each visit, the ACPR rate with 95% confidence intervals will be provided using Pearson-Clopper method for each treatment group.

Handling of missing values/censoring/discontinuations

Data will be handled as follows for ACPRs (PCR corrected or uncorrected):

- Presence of parasitemia which were determined to be reinfection on Day 8 or later will be counted as responders for PCR corrected ACPR and as non-responder for PCR uncorrected ACPR from the day of test
- Presence of parasitemia which cannot be determined to be recrudescence or reinfection due to missing PCR data will be counted as non-responders from the day of test
- Missing/underdetermined responses at a visit due to missing blood smear data at the visit will be counted as non-responders (PCR corrected or uncorrected) unless there is a later blood smear test indicating no parasitemia
- Patients who received non rescue anti-malarial medication will be considered in the analysis as if they had not taken the antmalarial drug

In addition, PCR-corrected and uncorrected ACPR rate will be calculated and plotted using the Kaplan-Meier method for each treatment group in the FAS (see [Section 2.5.4](#)).

2.7.2.2 Treatment failure related parameters

For the following parameters, 95% confidence intervals will be provided for each treatment group using the Pearson-Clopper method:

- proportion of patients with parasitemia at 12, 24, and 48 hours after treatment
- proportion of patients with early treatment failure (ETF)
- proportion of patients with late clinical failure (LCF)
- proportion of patients with late parasitological failure (LPF)

The above parameters will be determined using the uncorrected asexual parasite counts.

In addition, patients whose outcome status cannot be determined due to incomplete/missing data will be excluded from analysis. Especially, the denominator is the number of patients who experience treatment failure or have malaria blood film result at Day 43 for LCF and LPF.

In planned analysis of PCR uncorrected ACPR at Day 29, administration of non-study antimalarial drugs without treatment failures was not considered. A sensitivity analysis will be performed to assess the impact of administration non-study antimalarial drugs on the PCR uncorrected response rate. Proportion of patients with PCR uncorrected ACPR at Day 29 with 95% CI will be re-calculated by considering the patients receiving non-study antimalarial drugs if received before Day 29 without being treatment failures as non-responder using FAS for PK Run-in, Part A and B. Patients who received concomitant prohibited non-malaria medications with potential impact on efficacy/antimalarial activity (PROH01b) before the Day 29 visit without being treatment failures will be considered as as non-responder also.

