## 4 Population

The study population will consist of male and female patients (PK Run-in Part and Part A:  $\geq 12$  years old and  $\geq 35.0$  kg; Part B: 2 to < 12 years old and  $\geq 10.0$  kg) with confirmed and uncomplicated *P. falciparum* malaria.

Only patients with malaria symptoms and *P. falciparum* counts more than 1000 and less than 150 000 parasites/ $\mu$ L will be included in the study.

The plan is to enroll and treat 12 patients in PK Run-in Part and to randomize approximately 500 patients (325 in Part A and up to 175 in Part B) in approximately 15 sites in Africa and Asia. Expected recruitment in Africa is approximately 85% for both Parts A and B with the rest of the patients expected to be recruited in Asia. The expected drop-out rate is 16% ([Held et al 2015](#)).

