2.1.1.1 Definition of treatment failures

Early Treatment Failures (ETF)

Patient will be classified as ETF upon meeting any of the following criterion

- Development of danger signs or severe malaria on Day 2, Day 3, Day 4 in the presence of parasitemia.
- Parasitemia on Day 3 higher than Day 1 count irrespective of axillary temperature.
- Parasitemia on Day 4 with axillary temperature $\geq 37.5^{\circ}\text{C}$.
- Parasitemia on Day 4 equals to or more than 25% of count on Day 1.

Late Clinical Failure (LCF)

Patient will be classified as LCF upon meeting any of the following criterion

- Development of danger signs or severe malaria on any day from Day 5 to Day 43 in the presence of parasitemia without previously meeting any of the criteria of early treatment failure.
- Presence of parasitemia and axillary temperature $\geq 37.5^{\circ}\text{C}$ on any day from Day 5 to Day 43 without previously meeting any of the criteria of Early Treatment Failure.

Late Parasitological Failure (LPF)

- Presence of parasitemia on any day from Day 8 to Day 43 and axillary temperature $< 37.5^{\circ}\text{C}$ without previously meeting any of the criteria of Early Treatment Failure or Late Clinical Failure. Missing body temperature assessment in presence of parasitemia will be classified as LCF.

Note: If the temperature is measured using other routes, such as oral/tympanic/rectal, the corresponding threshold for fever is 38.0°C . Danger signs or severe malaria is recorded as adverse events. The adverse event start date of danger signs or severe malaria will be used in the determination of ETF and LCF. Only *P. Falciparum* asexual form is used for parasitemia/parasite in the assessments of treatment failure and ACPR in [Section 2.1.1.2](#) below. The body temperature assessment closest to the blood smear assessment date will be used.

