5.1.4 Visit windows

When visit windows are used, all visits will be re-aligned, i.e., they will be mapped into one of the visit windows. E.g., if the Day 4 visit of a patient is delayed and occurs on Day 7, say, it will be re-aligned to visit window Day 8. In the case of major deviations from the visit schedule, or due to unscheduled visits, several assessments of a patient may fall in a particular visit window (either scheduled or unscheduled). Statistical approaches to handle multiple assessments in a given visit window are specified below.

- Of note, patients are allowed to have gaps in visits. All data collected will be displayed in listings.
- Lower limit and upper limit of the Day 29 visit is set to be Day 25 and Day 33 respectively, according to the protocol visit schedule since this is the primary analysis timepoint.
- The following rules are used to determine the window for other visits post baseline:
 - “Lower limit” = “upper limit of prior applicable visit” + 1.
 - “Upper limit” = “target day of current visit” + integer part of (“target day of next applicable visit” – “target day of current visit”)/2 with the exception of Day 29
 - No upper limit for Day 43 visit
 - Upper limit of Day 15 is one day before the lower limit of Day 29

For assessments that are scheduled to be performed only once on a day, [Table 5-5](#) describes the analysis windows mapping to visits (not just scheduled visits) based on study days alone. For the assessments that may be performed on multiple timepoints on a day, [Table 5-6](#) describes the analysis windows mapping to visits based on study day and time. Repeat and/or unscheduled visits (which will be numbered in the database according to new NCDS standards) will be mapped for analysis purposes in the same way. If there are multiple measurements within an analysis window, the conventions defined in [Table 5-7](#) will be used to determine the appropriate measurement to be selected for analysis.

The mapped visits will be used in the by visit analyses. However, the listings will show the collected data regardless of used in the by visit analyses.

Table 5-5 Analysis visit windows based on study days alone

Analysis Visit	Target Day	Analysis window for assessment group		
		Vital signs/ Hematology/	Chemistry/ Urinalysis	Thyroid function
Baseline	1	Up to Day 1	Up to Day 1	up to day 1
Day 2	2	Day 2	NA	NA
Day 3	3	Day 3	NA	NA
Day 4	4	Day 4	NA	NA
Day 5	5	Days 5 - 6	NA	NA
Day 8	8	Day 7 - 11	NA	NA

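### The LCF and LPF denominator depends on the outcome, so both proportions tend to be modestly overstated when loss to follow-up is non-informative and spread over time

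*SAP*

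**What the plan says.** SAP 2.7.1 lists the proportions of patients with LCF and with LPF as secondary efficacy variables and names the population: "Analyses of other secondary efficacy variables will be based on the FAS".

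Both outcomes accrue over most of follow-up. LCF includes "Development of danger signs or severe malaria on any day from Day 5 to Day 43 in the presence of parasitemia". LPF is "Presence of parasitemia on any day from Day 8 to Day 43" without fever and without an earlier ETF or LCF.

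SAP 2.7.2.2 gives each proportion a Clopper-Pearson 95% interval per treatment group and sets two rules on who is counted. The general rule, also in Protocol 9.5.1.2, is that "patients whose outcome status cannot be determined due to incomplete/missing data will be excluded from analysis". The specific rule for LCF and LPF, found only in the SAP, is that "the denominator is the number of patients who experience treatment failure or have malaria blood film result at Day 43".

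The Day 43 film is defined more widely than the name suggests. SAP 5.1.4 states "No upper limit for Day 43 visit", and Table 5-6 maps every parasite count from Day 34 onward to that visit.

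On loss, Protocol Section 4 says "The expected drop-out rate is 16" per cent. Kaplan-Meier estimation with censoring is planned for corrected and uncorrected ACPR (SAP 2.5.4.1, 2.5.4.2), recrudescence and reinfection (2.7.2.4, 2.7.2.5). SAP Table 2-6 marks none for LCF or LPF.

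**The concern.** Take two patients last seen on Day 20. One had parasitaemia on Day 15 and is in the denominator as a failure. The other was clear throughout and is removed. Loss thus removes failure-free patients from the denominator but leaves in the failures already seen. The exact interval is then centred on a proportion from a set selected partly by outcome, not on the FAS that SAP 2.7.1 names.

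The size of the effect depends on how much loss an arm has and when, so two arms with equal true failure could show somewhat different rates. No other planned analysis estimates LCF or LPF separately with censoring.

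The same lost, failure-free patient is also handled in three ways: as a non-responder for ACPR (SAP 2.7.2.1), censored in the Kaplan-Meier analyses, and dropped here. The reported ETF, LCF, LPF and uncorrected Day 43 ACPR proportions therefore need not add to 100%.

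**Working it through.** **Inputs from the documents.** Loss 16% (Protocol Section 4); 50 randomised per KAF156/LUM-SDF arm, 42 in the per-protocol set (SAP Section 3); LCF from Day 5 and LPF from Day 8, both to Day 43; Day 43 film window from Day 34. The documents give no LCF or LPF rate and no timing of failure or loss, so those below are assumptions.

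**The plan's own figure.** 42/0.84 = 50, 21/0.84 = 25, and 6 × 50 + 25 = 325, as stated. The same 16% is called drop-out in Protocol Section 4 and per-protocol exclusion in the sample size section. True loss before Day 34 may be lower, so 5% is also shown.

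**Estimator.** Let p be the true proportion of each outcome and s the share of patients still followed when it is seen. For failure type k, the SAP proportion has expectation

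p_k s_k / (p_ETF s_ETF + p_LCF s_LCF + p_LPF s_LPF + p_0 s_0),

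where p_0 is the failure-free proportion and s_0 the share of those patients with a film in the Day 43 window. The bias is zero only if s_k equals the average s in the denominator.

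**Evenly spread, non-informative loss.** Assume one failure type with true rate 10%, uniform over Days 8–43 (mean 25.5), and 16% loss uniform over Days 4–43.

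- Failures seen: 0.10 × [1 − 0.16 × (25.5 − 4)/39] = 0.0912.
- Film required at Day 43 itself: failure-free retained 0.90 × 0.84 = 0.756, giving 0.0912/(0.0912 + 0.756) = 10.8%.
- Everyone present on Day 34 retained: failure-free 0.90 × [1 − 0.16 × 30/39] = 0.789, plus 0.0005 for patients lost after Day 34 ahead of a later failure. This gives 0.0912/0.881 = 10.35%.

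The second case is the mildest, because it assumes that each such patient has a film. Scheduled visits fall on Days 25–33 and 39–47, so on Days 34–38 only an unscheduled or withdrawal film would count. A true 20% becomes 21.3% or 20.6% on the two readings.

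**Visit-based simulation, LPF the only failure type, 16% loss:**

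| True LPF | SAP rule | Failures/FAS | Kaplan-Meier |
|---|---|---|---|
| 5% | 5.3% | 4.5% | 5.0% |
| 10% | 10.6% | 8.9% | 10.0% |
| 20% | 21.0% | 17.9% | 20.1% |
| 30% | 31.3% | 26.7% | 30.0% |

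With 5% loss the excess is 0.1 to 0.4 points.

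**Loss after most failures.** With LCF 5%, LPF 15%, all failures at Day 29 and all 16% loss later, the denominator is 0.20 + 0.80 × 0.84 = 0.872. LPF becomes 0.15/0.872 = 17.2% and LCF 0.05/0.872 = 5.7%. The largest excess found was 2.3 points (LPF 30.0% to 32.3%).

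**Where the bias vanishes or reverses.**

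- All loss before Day 5: every s is 0.84, so LPF is 0.126/0.84 = 15.0%, unchanged.
- All LPF found at the Day 43 visit, loss evenly spread: LPF is 0.126/0.850 = 14.8% against a true 15.0%, while LCF rises from 5.0% to 5.7%.
- Lost patients at 1.5 times the failure risk: true 10.8%, SAP rule 10.8%. At twice the risk: true 11.6%, SAP rule 11.1%, Kaplan-Meier 10.5%.

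**The case against.** The strongest reply is that the effect is small and little hangs on it. With 50 patients in an arm, one patient is 2 points and the exact 95% interval for 5/50 runs from 3.3% to 21.8%; an excess below one point is less than half a patient. SAP 2.7.2 sets no hypotheses for secondary endpoints. Table 2-6 plans neither a between-arm comparison nor a pooled analysis of LCF or LPF. The primary Day 29 test and the Part B efficacy criterion in Protocol Table 3-2 do not use them. Total uncorrected failure already has a censored analysis. All of this stands and limits the importance of the point. It does not make the denominator sound. Protocol 3.3 also lets secondary efficacy parameters help to discriminate between Part A cohorts, although the SAP's interim list does not name LCF or LPF.

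Three stronger readings are tempting, but the documents do not support them.

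- **Both rates are certain to be overstated.** The direction depends on when failure and loss occur and on the risk of lost patients. The documents give none of these.
- **Only patients who complete Day 43 count among non-failures.** The window admits any film from Day 34.
- **The bias is the gap from failures/FAS.** If 8 of 50 are lost failure-free, 5/42 = 11.9% against 5/50 = 10.0%, a ratio of 1.19. But failures/FAS treats every lost patient as a non-failure and is itself too low.

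**Conclusion.** The point holds in a limited form. The rule makes inclusion depend on outcome, and under non-informative loss spread over follow-up it pushes LCF and LPF upward. The excess is about 0.3 to 0.8 points at a true 10% with 16% evenly spread loss, about 2 points if loss follows most failures, and a few tenths at most with 5% loss. These sizes rest on assumed failure rates and timing and on taking the 16% as loss to follow-up. Very early loss, LPF found mainly at Day 43, or higher risk among lost patients would remove or reverse the bias. A reader might infer that the efficacy conclusion or the choice of Part B doses is compromised; the documents do not support that, because the primary test and the efficacy criterion use Day 29 PCR-corrected ACPR. This is a correction to descriptive secondary results that is worth making because it is cheap.

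**What to change.** Replace the LCF and LPF denominator rule in SAP 2.7.2.2 with the Day 43 cumulative incidence of each in the FAS. Censor patients without failure at their last parasite assessment, and treat the other failure types as competing events.

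The time-to-event data of SAP 2.5.4.2 can be adapted but not used as they stand. They need a failure-type flag and their own event and censoring rules. At present never-cleared patients are given an event at Day 7, and patients are censored at infection with another species and at non-rescue antimalarials. The text should also say that the first failure sets the type, because the LCF definition excludes only an earlier ETF.

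Censoring too assumes non-informative loss, and at twice the risk it lay further from the truth than the SAP rule. So also report, per arm, the number of patients lost failure-free, with bounds counting them all as non-failures and all as failures. With 5 failures and 8 lost among 50, the bounds are 5/50 = 10% and 13/50 = 26%.

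The cost is one SAP paragraph and one table, with no new data collection.
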